- B) Premenopausal patients who have de-novo metastatic disease (metastatic disease at presentation).
- C) Premenopausal women who have not received Tamoxifen in the metastatic setting, but have received up to two lines of chemotherapy.

Post-Menopausal Women or Men

- D) Postmenopausal patients who have progressed on first-line or second-line therapy with an aromatase inhibitor in the metastatic setting
- E) Postmenopausal patients who have recurred while on or after completion of adjuvant treatment with aromatase inhibitors (they have completed at least one year of adjuvant AI in the adjuvant setting before progression on AI).
- F) Postmenopausal patients who are not considered candidates for treatment with an aromatase inhibitor by their oncologist , patients not willing not to go on to AI, or were intolerant to AI
- G) Post-menopausal women or men who have been treated with up to three lines in the escalation arm and up to two lines of chemotherapy in the dose expansion arm in the metastatic setting.

Type of Study

Open labeled, non-randomized; phase I dose escalation followed by phase Ib dose expansion

Prior Therapy

- Progression on any aromatase inhibitor for metastatic disease
- Recurrence ≥ 12 months after commencement of adjuvant aromatase inhibitors
- Patients are allowed (but not required) to have up to two prior chemotherapy regimens for metastatic disease

Rationale for Study

Cell cycle progression is directly regulated by cyclin-dependent serine-threonine protein kinases. The cyclin D proteins are important in cancer, as their abundance and functions are regulated by extracellular growth factor and adhesion signaling. The cyclin D proteins act through the CDK4 and CDK6 protein kinases to promote G1 progression (1). CDK4 and CDK6, in turn, hyperphosphorylate and activate the retinoblastoma protein Rb to promote cell cycle entry and cell proliferation. Consistent with their having an important role in human cancer, focal copy number abnormalities that result in increased CDK activity are among the most commonly described genetic events observed in diverse tumor types; these events

include amplifications of the genes that encode cyclin D1 or CDK4, and deletions affecting the CDKN2A locus, which encodes the p16INK4a inhibitor of CDK activity (2-4).

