Multiple adjuvant studies have described amenorrhea as a positive prognostic factor in patients with overall survival after adjuvant chemotherapy. Based upon a number of adjuvant studies, the NCCN guidelines recommend goserelin to be strongly considered in premenopausal women who are menstruating despite receiving chemotherapy (7). In a retrospective study done at one hospital, over 150 patients with stage Ia to IIIa ER + breast cancer who received goserelin or chemotherapy were reviewed. Survival analysis was assessed by the Kaplan-Meier method. Survival at 11 years was significantly better in the goserelin group ($P < 0.0012$). The lifetime lost was lower in the goserelin group (42 months vs. 66 months). The quality adjusted survival (QAS) of patients who received goserelin was longer (122.5 ± 6.3 vs. 112.2 ± 6.7 months). The quality-adjusted life-year was higher in the goserelin group. Goserelin therapy results in better survival and higher utility-weighted life-years, and is more cost-effective (8). We plan to add goserelin to all women who are not postmenopausal. We estimate that of the 40 patients on study, approximately 20 will not meet the standard criteria of a post-menopausal state (no menstrual cycles for greater than 12 months and FSH of ≥ 40). We will not stratify for menopausal status. This

study is inclusive of all women regarding of menopausal status and explores the combination of Tamoxifen with this CDK4/6 inhibitor.

We will additionally explore two cohorts in the Phase Ib expansion. Having a continuous dosing cohort has multiple advantages. There is sustained inhibition of the cell cycle and less AEs. This cohort will allow us to further explore a cohort with increased safety and better patient compliance. Patients will not have to remember whether they are on the “on week” or the “off week.” Continuous dosing was done in Ph I CLEE011X2101 and both continuous and intermittent dosing revealed increased rates of grade 3 or 4 neutropenia rates at day 15 of every cycle on doses of 600 mg of Ribociclib and higher. **At lower doses, ribociclib had lower rates of neutropenia and continuous dosing should be tolerated.**

Type of Study:

Open labeled, non-randomized, Phase I escalation study with a Phase Ib dose expansion.

Phase I

The phase I portion of the study is a ***dose escalation*** to confirm the safety of the combination and to determine the MTD and the RP2D for ribociclib with Tamoxifen.

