Phase I will be conducted in all patients with HR+/HER2- locally advanced or metastatic breast cancer with any prior endocrine therapy and up to three prior cytotoxic chemotherapy regimens administered in the metastatic or locally advanced setting.

Phase Ib dose expansion

Phase I trials are increasingly including dose-expansion cohorts (Ib) after the maximum-tolerated dose (MTD) has been reached to better characterize the toxicity profile and identify early signs of efficacy within this specific disease population. Our goal is to assess the anti-tumor activity Ribociclib + Tamoxifen and to further evaluate their safety in adult patients with HR+/HER2- locally advanced or metastatic breast cancer. Patients in the phase 1b expansion will have the same exclusion and inclusion criteria except that they will only be allowed to have up to two lines of cytotoxic chemotherapy in the metastatic setting.

Tamoxifen will be administered orally according to the standard regimen used in clinical practice (20 mg oral QD). Ribociclib will be administered orally, once daily for 21 consecutive days followed by a 7-day planned break (28-day cycle). In the *continuous dose cohort*, ribociclib will be administered daily (QD) without a break in each cycle. Tamoxifen will be administered in combination with ribociclib until disease progression or if unacceptable toxicity occurs that precludes any further treatment and/or if

treatment is discontinued at the discretion of the investigator or the patient, or the patient's death, whichever occurs first.

Phase I Study drugs (ribociclib dose may change depending on results of phase I)

TAMOXIFEN: 20 mg po daily

RIBOCICLIB: Phase I: starting at a dose of 400 mg po for 21 days of a 28-day treatment cycle; increased to 400 mg po daily (continuous dosing); increased to 600mg po daily for 21 days of a 28 day cycle.

Phase 1b expansion will look at two cohorts: 600 mg po for 21 days of a 28 day cycle with Tamoxifen and a continuous dosing cohort of ribociclib 400 mg daily with Tamoxifen.

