Patient Population:

Patients with estrogen and/or progesterone receptor positive, HER2-negative advanced (metastatic) breast cancer that are in one of the following populations

Pre-menopausal Women:

- A. Pre-menopausal women who received adjuvant Aromatase Inhibitor and Ovarian Suppression (AI + OS) in the adjuvant setting and completed at least 12 months of hormonal therapy.
- B. Pre-menopausal women who have never been treated with endocrine therapy with de-novo metastatic disease.
- C. Pre-menopausal women who have not received Tamoxifen in the metastatic setting, but have received up to two lines of chemotherapy for dose expansion and up to three lines for dose escalation.

Post-Menopausal Women or Men

- D. Post-menopausal women or men who have progressed on first-line or second-line therapy with an aromatase inhibitor
- E. Post-menopausal women or men who have recurred while on or after completion of adjuvant treatment with aromatase inhibitors (they have completed at least one year of adjuvant AI in the adjuvant setting before progression on AI).
- F. Post-menopausal women or men who are not considered candidates for treatment with an aromatase inhibitor by their oncologist, refused AI, or intolerant to AI
- G. Post-menopausal women or men who have been treated with up to two lines of chemotherapy for dose expansion and up to three lines for dose escalation in the metastatic setting.

Total number of patients: 40

Number of Centers: 1 (will be adjusted, increased if accrual goals are not met).

Sample Size Justification (will be updated by statistician):

For a total of **40 subjects**, about 9-12 will be accrued during phase 1 portion and **about 30 patients for the phase 1b expansion.**

Part 1: phase 1 portion:

We will evaluate the first 9-12 patients in the phase I portion for safety.
The Primary objective is safety.

Part II: phase Ib expansion:

For the phase one expansion we will include pre- menopausal women, post-menopausal women, and men evaluated as one group. We will further evaluate both a three weeks on and one week off cohort (i.e. once daily for 21 consecutive days followed by a 7-day planned break) and a *continuous dose cohort* of ribociclib administered daily (QD) without a break in each cycle. Tamoxifen will be administered daily per standard of care in both cohorts.

The **primary objective** in the phase I study is to confirm safety, tolerability, confirm DLT, and determine the RP2D of Ribociclib with Tamoxifen

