 - b. Female sterilization (have had surgical bilateral oophorectomy with or without hysterectomy) or tubal ligation at least six weeks before taking study treatment. In case of tubal ligation alone, only when the reproductive status of the woman has been confirmed by follow up hormone level assessment.
 - c. Male sterilization (at least 6 months prior to screening). For female patients on the study, the vasectomized male partner should be the sole partner for that patient
 - d. No patients with HR+ disease should receive hormonal contraception, however the two following methods can be combined: Placement of an intrauterine device (IUD) or intrauterine system (IUS and barrier methods of contraception: Condom or Occlusive cap (diaphragm or cervical/vault caps) with spermicidal foam/gel/film/cream/ vaginal suppository.

Note: The use of oral contraception is not allowed.

Women are considered **post-menopausal** and not of child bearing potential if they have had 12 months of natural (spontaneous) amenorrhea with an appropriate clinical profile (e.g. age appropriate, history of vasomotor symptoms) or have had surgical bilateral oophorectomy (with or without hysterectomy) or tubal ligation at least six weeks ago. In the case of oophorectomy alone, only when the reproductive status of the woman has been confirmed by follow up hormone level assessment is she considered not of child bearing potential.]

- Patients who meet the eligibility criteria may be registered and enrolled on the trial. We will complete phase I portion of the study before proceeding to phase Ib expansion. At time of phase Ib expansion, we will alternate enrollment to both cohorts of our study, until both cohorts are complete.
- A signed copy of the institution's IRB-approved informed consent document must be placed on file.
- Patients must not start protocol treatment prior to registration.

7 TREATMENT PLAN:

Investigational Study Treatment

RIBOCICLIB will be supplied by Novartis or its designee in the form of 200 mg hard gelatin capsules/tablets as individual patient supply packaged in bottles.

All dosages prescribed and dispensed to the patient and all dose changes during the study must be recorded.

Dose and treatment schedule

Study treatment	Pharmaceutical form and route of administration	Dose	Frequency and/or Regimen
RIBOCICLIB	Capsules/tablets for oral use	400 mg	21 days on and 7 days off Or Daily (in continuous cohort)

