8 TREATMENT PLAN

Phase I/ Phase Ib dose expansion:

TAMOXIFEN: 20 mg PO daily will be given with RIBOCICLIB:

Ribociclib (LEE011)

In phase I: Ribociclib PO starting at a dose of 400 mg po for 21 days of a 28-day treatment cycle; this will be increased to 400 mg continuously. We will then evaluate 600 mg po daily for 21 days of a 28 day cycle if tolerated.

If there are no dose limiting toxicities, in the phase I portion, Tamoxifen 20 mg will be given with the MTD dose of Ribociclib in 15 patients. This is expected to be 600mg three weeks on and one week off. These patients will *not be stratified* for menopausal status.

If the 400mg continuous dose was well tolerated in the escalation arm, we will then expand this cohort in the phase Ib expansion, we will have an additional cohort of Tamoxifen 20 mg with 400 mg ribociclib in a continuous daily dose in an additional 15 patients. These patients will *not be stratified* for menopausal status.

Goserelin acetate (Zoladex) (3.6 mg subcutaneous every 28 days) will be given per NCCN guidelines to pre-menopausal and peri-menopausal. This will be given on day 1 of every cycle. We estimate that up to 20 of 40 patients on this protocol will require goserelin.

Goserelin is given if patient is premenopausal or peri-menopausal at the time of study entry.

Premenopausal status is defined as either:

- Patient had last menstrual period within the last 12 months.
- In case of therapy induced amenorrhea, with a plasma estradiol ≥ 10 pg/mL and/or FSH ≤ 40 IU/l or in the premenopausal range according to central laboratory definition.
- Patients who have undergone bilateral oophorectomy do not need goserelin.

Peri-menopausal status is defined as neither premenopausal nor postmenopausal (see exclusion criteria for definition).

8.1 Study Design:

Dose and Treatment Schedule – Table 8-1

No of pts	Cohort Level	RIBOCICLIB	Tamoxifen
3-6 (phase 1)	1	400 mg oral days 1-21, followed by 1 week break	20mg oral daily
3 -6 (phase 1)	2	400mg continuous	20 mg oral daily
3 -6 (phase 1)	3	600 mg oral day 1-21 followed by 1 week break	20 mg oral daily
15 (Ib dose expansion)	Phase Ib dose expansion	600 mg oral day 1-21 followed by 1 week break	20mg oral daily
15 (Ib dose	Phase Ib dose expansion-	400 mg oral daily	20 mg oral daily

expansion	continuous cohort	
------------------	--------------------------	--

Ribociclib Capsules/tablets for oral use 400 mg OR 600 mg Days 1-21 of each 28 day cycle or daily.

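### Phase Ib patients are assigned to the two ribociclib regimens by open alternation, so the informal safety and compliance comparison between regimens is open to selection bias

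*Combined protocol and SAP*

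**What the plan says.** The Synopsis (Type of Study) describes the trial as "Open labeled, non-randomized; phase I dose escalation followed by phase Ib dose expansion", and a second Type of Study entry in the Synopsis repeats that it is open label and non-randomized.

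For the expansion, the Synopsis states: "Phase 1b expansion will look at two cohorts: 600 mg po for 21 days of a 28 day cycle with Tamoxifen and a continuous dosing" (the latter at 400 mg daily). Section 8 and Table 8-1 give 15 patients to each; the second cohort is "ribociclib in a continuous daily dose in an additional 15 patients", opened if that regimen was well tolerated in escalation.

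The registration text after the exclusion criteria sets the assignment: "At time of phase Ib expansion, we will alternate enrollment to both cohorts of our study, until both cohorts are complete". Nothing in the protocol describes a random sequence, concealment or central release of assignments. On sites, the Synopsis says "Number of Centers: 1 (will be adjusted, increased if accrual goals are not met". On balance between cohorts it says "We will not stratify for menopausal status", and Section 8 repeats this for both cohorts.

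The Synopsis rationale for continuous dosing is comparative: "There is sustained inhibition of the cell cycle and less AEs", and "This cohort will allow us to further explore a cohort with increased safety and better patient compliance". The Synopsis secondary objective and Section 3.1 both look to the expansion cohorts to characterise toxicity.

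Section 8.6 dates the screening scan relative to randomisation, although no randomisation is described.

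**The concern.** With both cohorts recruiting at one open-label site in alternation, whoever registers the next patient can know which regimen is due. That person can then time a registration or choose which candidate to approach first.

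The protocol supplies a motive and the means. The Synopsis reports more grade 3 or 4 neutropenia at 600 mg and above, and less at lower doses, so an investigator could reasonably prefer the 400 mg cohort for a marrow-fragile patient. Expansion patients may have had none, one or two prior chemotherapy lines (Section 4), so they differ in ways staff can see. Baseline tests remain valid for 28 days (Section 8.5, footnote c), which leaves room to wait. Exclusion 9 in Section 5 rests on the investigator's judgement of safety risk and compliance, the same outcomes the Synopsis credits to continuous dosing. Section 11.3 requires unevaluable patients to be replaced but does not say where they join the alternation.

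If cohorts filled this way show different rates of neutropenia, dose reduction or compliance, a reader cannot tell a regimen effect from a difference in who was entered.

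**Working it through.** **1. The plan's own figure.** The only sized test is the single-arm response rule in Section 10.2: reject a 10% response rate if 8 or more of 40 respond, with 25% as the alternative. The exact binomial gives:
- P(X ≥ 8 | n = 40, p = 0.10) = 0.0419, matching the table's 0.042.
- P(X ≥ 8 | n = 40, p = 0.25) = 0.818, matching 1 − 0.182.

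The 0.045 in the text of Section 10.2 does not reproduce; that is a separate matter. The rule counts responders over all patients and does not use the cohort label. No figure is given anywhere for a comparison of the two cohorts.

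**2. How predictable is the next assignment?** There are 30 expansion assignments, 15 per cohort. Under alternation the first is a coin toss to the guesser and the other 29 are known:

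(0.5 + 29) / 30 = 98.3%.

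For randomised 15:15 schemes, suppose staff see past assignments and always guess the cohort with more places left in the block. Exact recursion gives:

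| Scheme | Share guessed, c | 2c − 1 |
|---|---|---|
| Blocks of 4 (last block of 2) | 71.1% | 0.422 |
| Blocks of 6 | 68.3% | 0.367 |
| One random 15:15 list | 59.9% | 0.197 |

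**3. What could this do to a safety contrast?** The documents give no inputs here, so these are assumptions: no true difference between regimens, and adverse event risk 0.60 in high-risk and 0.30 in other patients.

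Spurious difference = (0.60 − 0.30) × (difference in high-risk share between cohorts).

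- Shares 60% v 40% (9 v 6 of 15): 0.30 × 0.20 = 0.06, or 6 points. Check: 0.6 × 0.60 + 0.4 × 0.30 = 0.48, against 0.4 × 0.60 + 0.6 × 0.30 = 0.42.
- Shares 70% v 30%: 0.30 × 0.40 = 0.12, or 12 points.

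If staff can only guess, the expected difference shrinks by the factor 2c − 1 (right guesses minus wrong ones; alternation is treated as fully predictable). The 6 points become 2.5 with blocks of 4, 2.2 with blocks of 6 and 1.2 with a single list. The 12 points become 5.1, 4.4 and 2.4.

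**4. What would an unbiased contrast be worth?** For assumed rates of 60% v 30%, 15 per cohort and two-sided 0.05, power is 23% by exact Fisher test (37% by normal approximation). Planned drug per cycle also differs: 600 × 21 = 12,600 mg against 400 × 28 = 11,200 mg. Dose and schedule change together.

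**The case against.** The best defence is that this is an early-phase expansion, openly labelled non-randomized, with no planned inference between cohorts. Section 3 names no between-cohort comparison and no compliance endpoint, and the comparative language sits in the Synopsis rationale. Fifteen per cohort cannot give a precise contrast, and even perfect randomisation would compare two regimens, not isolate schedule. Alternation also balances numbers and calendar time. Nothing in the documents suggests that steering is likely, and the text says only that enrolment alternates; more centres might be added.

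Most of this stands, and it limits the weight of the point. It does not remove it. The Synopsis says what the continuous cohort is expected to show, and readers will set the two cohorts side by side. Low precision does not excuse an avoidable bias. Blocked randomisation also keeps numbers and calendar time close to balanced.

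Three stronger readings are tempting and are not supported:
- *The expansion is the only evidence on which schedule to take forward.* Escalation levels 2 and 3 are the same two regimens, Section 10.1 sets the recommended phase II dose from dose-limiting toxicities there, and no rule selects a schedule from expansion data.
- *The response conclusion is compromised.* The 8-of-40 rule pools patients regardless of cohort.
- *Possible imbalance in menopausal status counts against alternation.* Chance imbalance of that kind would be shared by unstratified randomisation.

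**Conclusion.** The point holds in a limited form. While both expansion cohorts are open, the next assignment can be known from the second patient on, and no safeguard is described. The informal comparison of safety, tolerability and compliance between the two regimens is therefore exposed to selection bias.

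The size is illustrative: 6 to 12 percentage points under the assumed high-risk shares and adverse event risks, neither of which comes from the documents. The conclusion assumes that alternation means taking turns patient by patient and that recruiting staff can see the sequence, as one open-label site would. It is an inexpensive improvement to the design; it does not invalidate the trial's planned analysis.

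**What to change.** Replace the alternation sentence in the registration text with:

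> While both expansion cohorts are open, patients are assigned 1:1 from a computer-generated list with randomly varying block sizes, concealed in the trial database and released only after registration. Replacement patients take the next assignment. If only one cohort is open, all patients enter it.

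Then:
- In both Type of Study entries in the Synopsis, say that phase Ib is randomised with no formal between-cohort test. This also reconciles the reference to randomisation in Section 8.6.
- Keep 15 + 15 and no stratification, as the Synopsis and Section 8 now state.
- Add to Sections 10.2 and 10.3 that any contrast between cohorts is descriptive, compares regimens (dose and schedule together) and has low precision at 15 per cohort.

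Because treatment is open label, staff will still see past assignments, so some guessing remains; larger blocks reduce it.

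The cost is one randomisation list, a few sentences and the loss of the non-randomized description. There are no extra patients or visits, and the 8-of-40 rule is unchanged.

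If the sponsor keeps alternation, the minimum is a statement that the cohorts are described separately with no inference between regimens, plus a screening log showing which cohort was due when each candidate was considered.

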7.1 Dose Modifications

Dose Limiting toxicity (DLT) is defined as an adverse event or abnormal laboratory value assessed as having a reasonable possibility of relatedness to the study medication, unrelated to disease, disease progression, inter-current illness, or concomitant medications that occurs within the first 28 days of treatment (cycle 1) with RIBOCICLIB and Tamoxifen and meets any of the criteria included in below [modification tables](#). National Cancer Institute Common Terminology Criteria for Adverse events (NCI CTCAE) **version 4.03** will be used for all grading.

In this study, a DLT will occur if CTCAE grade 4 neutropenia lasts more than 4 consecutive days, if CTCAE grade 3 thrombocytopenia is associated with clinically significant bleeding or if there is grade 4 thrombocytopenia. Please see the following table (7-1) for other DLT criteria.

Table 7-1 Criteria for defining dose-limiting toxicities

TOXICITY	DLT CRITERIA
Hematology	≥ CTCAE grade 4 neutropenia lasting more than 4 consecutive days
	CTCAE grade 3 thrombocytopenia with clinically significant bleeding
	CTCAE grade 4 thrombocytopenia
	Febrile neutropenia (decrease in neutrophils associated with fever, ANC <1.0 x 10 ⁹ /L, fever ≥38.5°C)
	CTCAE grade 4 lymphopenia lasting more than 7 consecutive days
Skin and subcutaneous tissue disorders	CTCAE grade 3 Rash > 7 days despite optimal management and does not resolve to Grade 0 or 1
	CTCAE grade 4 Rash that is thought to be related to study drug
	≥ CTCAE grade 3 photosensitivity
Metabolism	Grade 2 hyperglycemia (Fasting glucose 200 – 249 mg/dL) (confirmed with a repeat Fasting glucose within 24 hours) that does not resolve to Fasting glucose <200 mg/dL within 14 consecutive days (despite optimal oral anti-diabetic therapy, i.e. glimepiride, glibenclamide and/or metformin)
	Grade 3 hyperglycemia (Fasting glucose 250-499 mg/dL) (confirmed with a repeat Fasting glucose within 24 hours) for > 14 consecutive days despite optimal oral anti-diabetic treatment
	Grade 4 hyperglycemia (Fasting glucose >499 mg/dL)
	Hyperglycemia leading to diabetic keto-acidosis, hospitalization for IV insulin infusion, or non-ketotic coma
	CTCAE grade 3 amylase and/or lipase, not reversible to ≤ CTCAE grade 2 for > 7 consecutive days
Gastro-intestinal	CTCAE grade 4 amylase and/or lipase
	≥ CTCAE grade 3 vomiting ≥ 48 hrs despite optimal anti-emetic therapy
	≥ CTCAE grade 3 diarrhea ≥ 48 hrs despite optimal anti-diarrhea treatment
Hepato-biliary	≥ CTCAE grade 3 pancreatitis
	≥ CTCAE grade 3 total bilirubin
	≥ CTCAE grade 3 ALT lasting >4 days (isolated increases in AST without concomitant increases in ALT will not be considered dose-limiting, because of the non-specific nature of AST)
	≥ CTCAE grade 2 ALT with a ≥ Grade 2 bilirubin elevation of any duration
ECG QT Interval	≥ CTCAE grade 4 ALT of any duration
	QTc interval ≥ 501 ms on at least two separate ECGs
Renal	≥ CTCAE grade 3 serum creatinine
Events not described above	≥ CTCAE grade 3, except for the exclusions noted below
Exceptions to DLT criteria	Grade 3 alopecia
	CTCAE grade 3 fatigue < 5 days

	CTCAE Grade 3 laboratory abnormalities that are responsive to oral supplementation or deemed by the investigator to be clinically insignificant
	CTCAE grade 3 edema <48 hours
CTCAE version 4.03 will be used for all grading. Optimal therapy for vomiting or diarrhea will be based in institutional guidelines, with consideration of the prohibited medications listed in this protocol.	

Table 7-2 Dose modification guidelines

Ribociclib (LEE011) Dose		
Starting dose	600 mg 3 x 200 mg capsules/tablets	400 mg 2 x 200 mg capsules/tablets
First dose reduction	400 mg 2 x 200 mg capsules/tablets	200 mg 1 x 200 mg capsules/tablets
Second dose reduction	200 mg 1 x 200 mg capsules/tablets	N/A

There are no scheduled dose reductions for Tamoxifen.

Table 7-3 Ribociclib dose adjustment and management recommendation for hematological adverse reactions

Toxicity/Grade	Dose Adjustment and Management Recommendations
Thrombocytopenia	
Grade 1 ($\geq 75 \times 10^9/L$)	No dose adjustment required.
Grade 2 ($\geq 50 \times 10^9/L - < 75 \times 10^9/L$)	Dose interruption until recovery to grade ≤ 1 . Re-initiate ribociclib at the same dose.
Grade 3 ($\geq 25 \times 10^9/L - < 50 \times 10^9/L$)	Dose interruption until recovery to grade ≤ 1 . Re-initiate ribociclib at the same dose level. • If toxicity recurs at grade 3: temporary dose interruption until recovery to grade ≤ 1 and reduce ribociclib to the next lower dose level.
Grade 4 ($< 25 \times 10^9/L$)	Dose interruption until recovery to grade ≤ 1 . Re-initiate ribociclib at the next lower dose level. • If toxicity recurs at grade 4: discontinue ribociclib.
Absolute neutrophil count (ANC)	

Grade 1 ($\geq 1.5 \times 10^9/L$)	No dose adjustment required.
Grade 2 ($1.0 - <1.5 \times 10^9/L$)	No dose adjustment required.
Grade 3 ($0.5 - <1.0 \times 10^9/L$)	Dose interruption until recovery to $>1.0 \times 10^9/L$. Re-initiate ribociclib at the same dose level. • If toxicity recurs at grade 3: temporary dose interruption until recovery to $>1.0 \times 10^9/L$. If resolved in ≤ 7 days, then maintain dose level. If resolved in > 7 days, reduce ribociclib dose to the next lower dose level.
Grade 4 ($<0.5 \times 10^9/L$)	Dose interruption until recovery to $\geq 1.0 \times 10^9/L$. Re-initiate ribociclib at the next lower dose level. • If toxicity recurs at grade 4: temporary dose interruption until recovery to $\geq 1.0 \times 10^9/L$ and reduce ribociclib at the next lower dose level.
Febrile neutropenia	
Grade 3 ANC $<1.0 \times 10^9/L$ with a single temperature of $>38.3^\circ C$ ($101^\circ F$) or a sustained temperature of $\geq 38^\circ C$ ($100.4^\circ F$) for more than one hour	Dose interruption until improvement of ANC $\geq 1.0 \times 10^9/L$ and no fever. Restart at the next lower dose level. • If febrile neutropenia recurs, discontinue ribociclib.
Grade 4 Life-threatening consequences; urgent intervention indicated	Discontinue ribociclib.
Anemia (Hemoglobin)	
Grade 1 ($\geq 10.0 - LLN$ g/dL)	No dose adjustment required.
Grade 2 ($\geq 8.0 - 10.0$ g/dL)	No dose adjustment required.
Grade 3 (<8.0 g/dL)	Dose interruption until recovery to grade ≤ 2 . Re-initiate RIBOCICLIB at the same dose.
Grade 4 Life-threatening consequences; urgent intervention indicated	Discontinue ribociclib.

Table 7-4 Recommendations for ribociclib dose modification in case of hepatic toxicities

HEPATOTOXICITY (BILIRUBIN, SGPT/ALT, SGOT/AST)
TOTAL BILIRUBIN without ALT/AST increase above baseline value

Grade 1 ($>$ ULN – 1.5 x ULN) (confirmed 48-to 72hrs later)	Maintain dose level with LFTs monitored bi-weekly
Grade 2 ($>$ 1.5 – 3.0 x ULN)	Dose interruption of ribociclib If resolved to \leq grade 1 in \leq 21 days, then maintain dose level If resolved to \leq grade 1 in $>$ 21 days or toxicity recurs, then reduce 1 dose level If toxicity recurs after two dose reductions, discontinue ribociclib
Grade 3 ($>$ 3.0 – 10.0 x ULN)	Dose interruption of ribociclib If resolved to \leq grade 1 in \leq 21 days, lower 1 dose level of ribociclib If resolved to \leq grade 1 in $>$ 21 days or toxicity recurs, discontinue ribociclib
Grade 4 ($>$ 10.0 x ULN)	Discontinue ribociclib
	Confounding factors and/or alternative causes for increase of total bilirubin should be excluded before dose interruption/reduction. They include but are not limited to: evidence of obstruction, such as elevated ALP and GGT typical of gall bladder or bile duct disease, hyperbilirubinemia due to the indirect component only (i.e. direct bilirubin component \leq 1 x ULN) due to hemolysis or Gilbert Syndrome, pharmacologic treatment, viral hepatitis, alcoholic or autoimmune hepatitis, other hepatotoxic drugs. For patients with Gilbert Syndrome, these dose modifications apply to changes in direct bilirubin only. Bilirubin will be fractionated if elevated.

AST or ALT	
AST or ALT without bilirubin elevation $>$ 2 x ULN	
Same grade as baseline or increase from baseline grade 0 to grade 1 (confirmed 48 to 72 hrs later)	No dose adjustment required with LFTs monitored per protocol if same grade as baseline or bi-weekly in case of increase from baseline grade 0 to 1
Increase from baseline grade 0 or 1 to grade 2 ($>$ 3.0 – 5.0 x ULN) or from baseline grade 2 to grade 3 ($>$ 5.0 – 20.0 x ULN)	Dose interruption of ribociclib If resolved to \leq baseline value in \leq 21 days, then maintain dose level If resolved to \leq baseline value in $>$ 21 days or toxicity recurs, then reduce 1 dose level If toxicity recurs after two dose reductions or recovery to \leq baseline value is $>$ 28 days, discontinue RIBOCICLIB
Increase from baseline grade 0 or 1 to grade 3 ($>$ 5.0 – 20.0 x ULN)	Dose interruption of ribociclib until resolved to \leq baseline value, then lower 1 dose level of ribociclib If recovery to \leq baseline value is $>$ 28 days, discontinue ribociclib If toxicity recurs, discontinue ribociclib
Grade 4 ($>$ 20.0 x ULN)	Discontinue ribociclib
AST or ALT and concurrent Bilirubin	
AST or ALT \geq grade 2 ($>$ 3 x ULN) in patients with normal values at baseline and total bilirubin $>$ 2 x ULN or AST or ALT \geq grade 3 ($>$ 5 x ULN) in patients with grade 1 or 2 at baseline, and total bilirubin $>$ 2 x ULN	Discontinue ribociclib
Confounding factors and/or alternative causes for increased transaminases should be excluded before dose interruption/reduction. They include but are not limited to: concomitant medications, herbal preparations or dietary supplements, infection, hepato-biliary disorder or obstruction, new or progressive liver metastasis, and alcohol intake.	

Additional follow-up for hepatic toxicities

Hepatic toxicity monitoring includes the following LFTs: albumin, ALT, AST, total bilirubin (fractionated if total bilirubin $> 2 \times$ ULN), alkaline phosphatase (fractionated if alkaline phosphatase is grade 2 or higher) and GGT. For patients with Gilbert Syndrome: total and direct bilirubin must be monitored, intensified monitoring applies to changes in direct bilirubin only.

Close observation is recommended in case of AST, ALT, and/or bilirubin increase requiring dose interruption, which involves:

- Repeating liver enzyme and serum bilirubin tests **two or three times weekly**. Frequency of re-testing can decrease to once a week or less if abnormalities stabilize or return to normal values.
- Obtaining a more detailed history of current symptoms.
- Obtaining a more detailed history of prior and/or concurrent diseases.
- Obtaining a history of concomitant drug use (including non-prescription medications, herbal and dietary supplements), alcohol use, recreational drug use, and special diets.
- Ruling out acute viral hepatitis types A, B, C, D, and E; hepatotropic virus infections (CMV, EBV or HSV); autoimmune or alcoholic hepatitis; NASH; hypoxic/ischemic hepatopathy; and biliary tract disease.
- Obtaining a history of exposure to environmental chemical agents.
- Obtaining additional tests to evaluate liver function, as appropriate (e.g., INR, direct bilirubin).
- Considering gastroenterology or hepatology consultations.
- Assessing cardiovascular dysfunction or impaired liver oxygenation, including hypotension or right heart failure as possible etiologies for liver dysfunction.

